In order to capture possible adverse effects of trial participation, trial-emergent adverse events will also be reported as any untoward medical occurrences occurring, during the baseline/cross-sectional imaging period but not during the 48 hour windows following the administration of ¹⁸F-AV-1451 or Florbetapir F 18 injection. For this purpose, the baseline/cross-sectional imaging period will be defined as beginning with the signing of consent and ending 48 hours after the last of the screening/baseline procedures described in sections [7.1.1 – 7.1.3](#), including (but not limited to) neuropsychological testing, MRI, ¹⁸F-AV-1451 or Florbetapir F 18 injection PET scanning and lumbar puncture.

The end of study for the purpose of adverse event reporting is defined as 48 hours after the last administration (i.e., 18 month visit or early termination visit) of ¹⁸F-AV-1451.

Serious Adverse Event (SAE)

An SAE is an AE that results in one of the following outcomes or constitutes one of the following events:

- Death;
- Initial or prolonged inpatient hospitalization (other than that required by protocol; “social hospitalization” or any hospitalization for non-medical reasons does not constitute an SAE);
- A life-threatening experience (that is, immediate risk of dying);
- Persistent or significant disability/incapacity;
- Congenital anomaly/birth defect;
- Considered significant by the investigator for any other reason.

Important medical events that may not result in death, be life-threatening, or require hospitalization may be considered serious adverse drug events when, based upon appropriate medical judgment, they may jeopardize the patient and may require medical or surgical intervention to prevent one of the outcomes listed in this definition.

Unexpected Adverse Event

An unexpected adverse event is an adverse event not previously reported or an adverse event that occurs with specificity, severity or frequency that is not consistent with the current investigator’s brochure.

Relationship to Investigational Product

Investigators will be instructed to report their assessment of the potential relatedness of each adverse event to protocol procedure, concomitant medication and/or investigational product. The assessment of the relationship of an adverse event to the administration of the investigational product is a clinical decision based on all available information at the time of the completion of the eCRF.

Intensity/Severity of an Adverse Event

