3.2 Exploratory Phase, Longitudinal Objectives

The primary objective of the longitudinal component is:

- To assess the rate of change of tau deposition as measured by Flortaucipir uptake over time

The exploratory objectives of the longitudinal component are:

- To explore associations between changes in Flortaucipir uptake in the brain and clinical and functional measures, as well as, biomarkers of neurodegeneration and neurological disease (CSF markers including tau, phospho-tau and beta-amyloid (AB), genetic markers, PET amyloid imaging, and brain atrophy assessed by volumetric MRI)
- To expand the Flortaucipir safety database

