4 STUDY DESIGN

4.1 General Design

This study is an open label, multicenter Phase 2 study. This study is conducted in two phases, an exploratory (first) phase and complimentary (second) phase. The study will enroll cognitively healthy volunteers, subjects with mild cognitive impairment (MCI) and subjects with Alzheimer's disease. Approximately 230 subjects will be enrolled in the study: 80 cognitively healthy volunteers (20 subjects who will be ≥ 20 to ≤ 40 years of age, and 60 subjects who will be ≥ 50 years of age), 80 subjects with MCI, 70 subjects with AD (60 subjects with a Mini-Mental State Examination (MMSE) ≥ 20 , and 10 subjects with an MMSE > 10 and < 20). For the 60 cognitively healthy volunteers ≥ 50 years of age, these subjects will be distributed across age deciles (50-59, 60-69, 70-79 and > 80).

All subjects will provide informed consent before starting any study procedures.

Screening assessments may take place over several days and will include demographic information, cognitive testing, safety assessment, and MRI, including both volumetric and standard clinical sequences. Subjects who qualify for the study will undergo both a florbetapir F 18 PET imaging session and a Flortaucipir PET imaging session. The imaging sessions must be performed at least 48 hours apart, but not more than 60 days apart. The order of the scans is interchangeable. Some subjects, who are ≥ 50 years of age, will have the option to also participate in cerebrospinal fluid (CSF) collection by lumbar puncture (LP).

Subjects who are ≥ 50 years of age will return for have a follow-up visits at 9 (+/-2) months 18 (+/-2) following the initial Flortaucipir scan. Cognitive assessments and updates to concomitant medications and medical history will be collected at each follow-up visit. Subjects will also have follow-up Flortaucipir scans and MRI, including both volumetric and

standard clinical sequences. A sub-set of subjects may have the option to have an additional resting state functional (rsf) MRI sequence scan in addition to the volumetric and standard clinical sequences at both the screening MRI and follow-up MRIs. Subjects or their designated decision maker will be contacted by phone at 5 and 14 months following the initial Flortaucipir scan to collect updated concomitant medications and medical history.

Florbetapir F 18 PET Imaging Session:

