6.2.2 Windows

No window algorithm is being used for this study.

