All values will be summarized by the four diagnostic groups: young cognitively normal (YCN) subjects (healthy volunteers ≥ 20 years of age and ≤ 40 years of age), old cognitively normal (OCN) subjects (healthy volunteers ≥ 50 years of age), patients with AD, patients with MCI, and overall. Frequency distributions including counts and percentages will be included for all categorical outcomes. Summary statistics including mean, standard deviation, median, minimum and maximum values will be presented for all continuous outcomes. Unless otherwise specified, hypothesis testing will be two-sided with type I error rate of 0.05.

All statistical analyses will be performed using SAS® version 9.3 or higher.

7.2 **Adjustments for Covariates**

Not applicable for the primary analyses.

7.3 **Handling of Dropouts or Missing Data**

Dropout subjects will not be replaced in this study. For situations with no rules for handling missing data, the default will be no imputation.

A likelihood-based mixed effects model for repeated measures will be used to handle missing longitudinal follow up cognitive measurements, or flortaucipir SUVr data. The model parameters are simultaneously estimated using restricted likelihood estimation incorporating all of the observed data. Estimates have been shown to be unbiased when the missing data are missing at random and when there is ignorable non-random missing data.

Repeated measures analyses will only use data from visits where the data was scheduled to be collected. When subjects discontinue from the study early, there may be efficacy data measurements at visits where the variables were not scheduled to be collected. These data will appear in listings only.

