8.6.2 Exploratory Phase, Longitudinal Analysis

8.6.2.1 Analysis of Primary Efficacy Variable

Mixed Model Repeated Measures for Evaluation of Flortaucipir SUV_r over time

Descriptive summary statistics for Flortaucipir SUV_r will be provided by amyloid beta status (AB+, AB-) at baseline, 9 month, and 18 month across all subjects.

Change from baseline for Flortaucipir SUV_r will be estimated using repeated measures models for all subjects except for YCN subjects (who do not have follow-up flortaucipir scans at 9 months and 18 month). Due to the concern of unequal variance for flortaucipir SUV_r changes by amyloid status, the model will be run for AB+ subjects only, and for AB- subjects only separately. For this analysis, time will be considered to be categorical variable. A mixed model will be run with MUBADA SUV_r change from baseline as dependent variable, baseline MUBADA SUV_r and age, and visit as independent variables. In order to appropriately model the within subject covariance, the covariance structure must be pre-specified. Each model should be fit using the unstructured covariance structure. If this structure does not converge, covariance structure in the order as auto-regressive, Toeplitz structures and the compound symmetry will be used.

The LS means of MUBADA SUV_r change at each visit from the model will be displayed along with the corresponding 95% confidence intervals. In addition, p-values will be

provided for testing that whether or not the LS means at each visit is significantly different than zero.

Spaghetti plots will be generated to display the relationship of Flortaucipir SUVr change across the follow up visits, by each subject. The plot will use MUBADA SUVr as y-axis, subjects' age at each visit as x-axis, and color code according to amyloid status.

Explore Factors Associated with Flortaucipir SUVr Change using Multivariate Analysis

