The analysis will be completed for AB+ subjects. A multivariate step wise selection regression model will be used to explore factors associated with the change in Flortaucipir SUVr (MUBADA). The dependent variable will be Flortaucipir SUVr (MUBADA) change at 18 months. The independent variables include baseline information such as age, cognitive assessments (MMSE), APOE4 status (carrier or non-carrier), florbetapir SUVr, and flortaucipir MUBADA SUVr. The significance level of entry and stay in the model will be both set as 0.2. For each variable in the final model, the parameter estimate, SE, 95% CI and associated p-value will be reported.

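### The longitudinal primary objective is a rate of tau change, but protocol and SAP estimate it as change at nominal 9- and 18-month visits, so the result is not expressed per unit of actual time

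*SAP*

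**What the plan says.** SAP 3.2 gives the longitudinal component one primary objective: "To assess the rate of change of tau deposition as measured by Flortaucipir uptake over time". Protocol 2.2 and 8.1.3.1 state the same objective.

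SAP 8.6.2.1 serves it with a mixed model for repeated measures (MMRM), fitted separately in amyloid-positive (AB+) and amyloid-negative (AB-) subjects. The outcome is change from baseline in MUBADA SUVr. The predictors are baseline SUVr, age and visit, and "For this analysis, time will be considered to be categorical variable". The output is the least-squares mean (LS mean) "change at each visit from the model will be displayed along with the corresponding 95% confidence intervals", with a test of each mean against zero. Protocol 8.1.3.1 also prescribes an MMRM with visit as a category.

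The same SAP section adds a stepwise regression in AB+ subjects: "The dependent variable will be Flortaucipir SUVr (MUBADA) change at 18 months".

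On timing, SAP 4.1 plans "follow-up visits at 9 (+/-2) months 18 (+/-2) following the initial Flortaucipir scan", and SAP 6.2.2 adds "No window algorithm is being used for this study". SAP 7.3 limits repeated-measures analyses to scheduled visits. Of efficacy measurements that early leavers have outside that schedule, it says "These data will appear in listings only".

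**The concern.** A rate has units of SUVr per unit of time. Neither the MMRM nor the regression contains elapsed time, and the SAP specifies no slope or annualised change. The visit label stands in for time, yet two subjects with the same label can have been followed for intervals that differ by four months.

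Two things are at stake. First, a reader who wants the rate must divide the LS mean by 9 or 18 months, and that is right only if scans centre on those months. Second, in the AB+ regression, differences in follow-up length add variation to the outcome that has nothing to do with how fast tau accumulates. If lateness happened to track a predictor such as baseline MMSE, that variation would become bias. The documents give no evidence either way.

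**Working it through.** The documents give no sample size, assumed rate or SD for the longitudinal objective, so there is no planned figure to reproduce.

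**Inputs.** Scan windows of 9 ± 2 and 18 ± 2 months (Protocol 7.1.4; SAP 4.1), that is 7 to 11 and 16 to 20 months. Assumption: a constant true rate *r* for each subject, so that change = *r* × actual months.

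**Spread within one visit label.** For two subjects with the same rate:
- first visit: 11*r* / 7*r* = 1.57
- second visit: 20*r* / 16*r* = 1.25

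**Error in an individual's rate.** Dividing change by nominal time has relative error (actual months / nominal months) − 1:
- first visit: 7/9 − 1 = −22.2%; 11/9 − 1 = +22.2%
- second visit: 16/18 − 1 = −11.1%; 20/18 − 1 = +11.1%

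**Error in a group mean.** Only the average shift in timing matters. For a mean shift of *s* months the error is *s* / nominal months:

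| Mean shift | 9-month visit | 18-month visit |
|---|---|---|
| 0 (symmetric timing) | 0% | 0% |
| ± 1 month | ± 11.1% | ± 5.6% |
| ± 2 months | ± 22.2% | ± 11.1% |

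**Simulation on assumed values.** Setup: 80 subjects, true rate 0.05 SUVr per year, between-subject slope SD 0.05 per year, scan noise SD 0.03, and 3,000 repetitions. The mean 18-month change divided by 1.5 years was compared with a generalised least-squares estimate of the random-slope model on actual time, with variances taken as known.

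| Scan timing | 18-month mean / 1.5 | Time-based slope |
|---|---|---|
| Uniform over 7–11 and 16–20 months | 0.0501 (SE 0.0065) | 0.0501 (SE 0.0065) |
| Uniform over 9–11 and 18–20 months | 0.0527 (+5.5%) | 0.0500 |

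True rates of 0.03 and 0.10, and scan noise of 0.06 at a rate of 0.05, gave the same pattern. With late scans the nominal-time figure was 5.5% to 6.1% too high, while the time-based slope stayed within 0.6% of the truth. With even timing the two SEs differed by about 1% or less. The gain is therefore correct units and robustness to timing, not precision.

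**Where timing does appear.** SAP 6.2.1 derives a relative day from actual dates. SAP 8.6.2.1 plans a per-subject plot of SUVr against age at each visit. Neither enters an SUVr estimate. The age that SAP 6.3 defines is imputed from birth year and truncated to whole years, too coarse for a rate if the same definition is used at visits. SAP 8.6.2.4.2 uses visit dates to compute person-years for clinical events, so the dates needed are in the database.

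**The case against.** The strongest reply is that the documents define their own answer. Protocol 8.1.3.1 restates the rate objective and then prescribes change at each follow-up visit with categorical visit. On time, the SAP follows the protocol. Mean change over a nominal 18 months, with a confidence interval, is a usable summary. It avoids assuming linear accumulation from at most three scans, and this is a hypothesis-generating phase. The ± 2-month windows do bound scan timing in the field; SAP 6.2.2 says only that no algorithm reassigns scans to visits. Nothing suggests that visits run systematically early or late. All of this stands. It limits the size of the point but does not supply a quantity per unit of actual time.

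Three stronger readings are tempting, and the documents do not support them.

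- *The objective gets no estimate.* It gets one, LS mean change at two nominal times. What is missing is its expression per unit of actual time.
- *Different timing biases an AB+ versus AB- contrast.* SAP 8.6.2.1 fits the two groups separately, tests each mean only against zero, and restricts the regression to AB+. It specifies no such contrast for SUVr change.
- *Early leavers' scans are discarded in quantity.* The 20% dropout in Protocol 8.1.1.2, applied to the 60 + 80 + 70 = 210 exploratory subjects aged 50 or over, suggests 42. That rate is a confirmatory-phase assumption, and 42 would count leavers, not unused scans. The final evaluation in Protocol 5.5 does not mention PET. The phrase "i.e., 18 month visit or early termination visit" in Protocol 7.7.2 belongs to a cut-off for adverse-event reporting, and the flow charts schedule no early-termination scan. Scheduled scans of leavers, such as one at 9 months, stay in the MMRM. The number of unused scans could be zero.

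**Conclusion.** The point holds as a mismatch between objective and estimate that is present in both documents. It is not a SAP departure from the protocol. A rate is asked for, and change at nominal visits is delivered.

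The size depends on visit timing, which the documents do not report. For the group mean the effect is about zero if timing is symmetric, and about 11% (first visit) or 5.6% (second visit) per month of average shift. For individuals it is up to 22% and 11%, and this stays as noise in the AB+ regression outcome even when timing is symmetric. These figures assume constant accumulation within a subject; the simulation also rests on assumed SDs and rates. The point does not invalidate the planned MMRM. It is a worthwhile, low-cost improvement that would let the study answer its rate question in the units of that question.

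**What to change.** - **SAP 8.6.2.1, primary model.** Keep the categorical-visit MMRM. Add a random-intercept, random-slope model of MUBADA SUVr on actual years from the initial flortaucipir scan, fitted separately in AB+ and AB-. Report the annualised slope with its 95% confidence interval as the estimate for the rate objective.
- **SAP 8.6.2.1, AB+ regression.** Use 18-month change divided by the actual years between the two scans as the dependent variable.
- **SAP 7.3.** State that any valid off-schedule flortaucipir scans, if they exist, enter the time-based model at their actual dates.

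The cost is SAP wording and one additional model on dates already collected. The statistical price is a linearity assumption over 18 months. The retained MMRM can check it: if accumulation is linear and scans centre on their nominal months, the 18-month LS mean should be about twice the 9-month one.

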4.5 Determination of Sample Size

A total of 230 subjects (80 cognitively healthy volunteers, 80 MCI and 70 AD) will be enrolled in the Exploratory Phase of this study. To explore the Flortaucipir SUVR values across age strata among cognitively healthy subjects, these subjects will be divided into 5 age groups as 20-40 years old, 50-59 years old, 60-69 years old, 70-79 years old and 80 years old or above. There will be 15 subjects in each of the 50 or older age groups and about 20 subjects from age group 20-40 years old. From a preliminary analysis of study T807000, the standard deviation (SD) of SUVR from combination region of interest (ROI) was 0.06 for subjects with low probability of AD. Therefore assuming a 0.06 SD, a sample of 15 subjects will give an approximately 90% probability to observe a 95% confidence interval as accurate as +/-0.04 around the point estimation.

From previous studies, the amyloid positive rate is approximately 50% among MCI patients and approximately 80% from AD subjects. Therefore 80 MCIs and 70 ADs will likely result in 40 amyloid positive MCIs and 56 amyloid positive ADs. Also from study T807000, the combination ROI SUVR difference between CN and AD was 0.39, with a pooled SD of 0.27. Assume a pooled SD of 0.30, a sample of 60 CNs and 56 amyloid positive ADs will give a 90% power to detect a 0.18 difference between the CN and AD groups.

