8.6.2.4.5 Multi-variate models to explore possible factors for cognitive impairments changes

The analysis will be completed for AB+ subjects. A multivariate step wise selection regression model will be used to explore factors associated with the change in psychometric score change at 18 months. The dependent variable will be each of these psychometric score change at 18 months respectively: ADAS Cog 11, MMSE, and FAQ. The independent variables include baseline information such as psychometric score (baseline ADAS Cog-11, MMSE, or FAQ), age, ANART score, APOE4 status (carrier or non-carrier), florbetapir SUVr, and flortaucipir MUBADA SUVr. The significance level of entry and stay in the model will be both set as 0.2. For each variable in the final model, the parameter estimate, SE, 95% CI and associated p-value will be reported.

Scatter plots will be generated for the following scenarios:

1. Change of ADAS score at 18 month versus Flortaucipir MUBADA SUVr score at baseline by each diagnostic groups.
2. Change of MMSE score at 18 month versus Flortaucipir MUBADA SUVr score at baseline by each diagnostic groups.
3. Change of FAQ score at 9 month or 18 month versus Flortaucipir SUVr score at baseline by each diagnostic groups.

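### The tau-change factor model (SAP 8.6.2.1) reports a baseline-SUVr coefficient that shared scan error pushes downward, by an amount the documents do not let us fix

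*SAP*

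**What the plan says.** SAP 8.6.2.1 has two parts. The first is a mixed model for MUBADA SUVr "change from baseline as dependent variable", with baseline SUVr, age and visit as covariates. The second is a stepwise factor model. For that model:

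- Population: "The analysis will be completed for AB+ subjects".
- Outcome: "The dependent variable will be Flortaucipir SUVr (MUBADA) change at 18 months". This sentence does not restate the reference point, but the section's change is change from baseline.
- Candidates: "The independent variables include baseline information such as age, cognitive assessments (MMSE), APOE4 status (carrier or non-carrier), florbetapir SUVr, and flortaucipir MUBADA SUVr".
- Selection: "The significance level of entry and stay in the model will be both set as 0.2".
- Reporting: "For each variable in the final model, the parameter estimate, SE, 95% CI and associated p-value will be reported".

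SAP 8.6.2.4.5 uses the same structure for 18-month change in cognitive and functional scores: "The independent variables include baseline information such as psychometric score (baseline ADAS Cog-11, MMSE, or FAQ), age, ANART score", followed by genotype and the two baseline SUVr values.

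Neither document gives a test-retest error for SUVr, a measurement-error correction, a caution about regression to the mean, or an alternative outcome for this model.

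**The concern.** The outcome is X18 - X0 and one predictor is X0. A baseline scan that reads high by chance raises the predictor and lowers the outcome, and a scan that reads low does the reverse. This produces a negative slope even when starting tau has nothing to do with later accumulation.

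The reported p-value is computed against a slope of zero. If the coefficient is read as a statement about true tau, that is the wrong reference value. Two misreadings follow: that subjects with more tau at the start accumulate less, or that starting tau does not matter when in fact it predicts faster accumulation. The lenient entry and stay level of 0.2 makes it easier for the artefact to be retained and reported.

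**Working it through.** **Inputs**

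- Sample: SAP 4.5 states "Therefore 80 MCIs and 70 ADs will likely result in 40 amyloid positive MCIs and 56 amyloid positive ADs", so 40 + 56 = 96. With 20% dropout, 96 x 0.8 = 76.8, or 77. The 20% is from Protocol 8.1.1.2 for the Confirmatory Phase and is borrowed here. The number of amyloid-positive older healthy subjects is not given and is left out.
- Baseline SD, S = 0.30: SAP 4.5. It is for the combination ROI, not MUBADA with the white-matter reference of SAP 6.4.1.1, so it is a stand-in.
- Scan-error SD, e = 0.03, 0.045, 0.06: assumed. The top value equals the total SD that SAP 4.5 gives for low-probability subjects.
- SD of true 18-month change, 0.05: assumed.

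**The plan's own figure.** SAP 4.5 claims 90% power for a 0.18 difference with 60 and 56 subjects. 0.18 / (0.30 x sqrt(1/60 + 1/56)) = 3.23, and Phi(3.23 - 1.96) = 0.90. It reproduces, but it only checks the SD and the group sizes. The factor model has no stated power.

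**Expected slope.** Write X0 = T0 + e0, true slope b, and reliability L = 1 - e²/S². The expected slope of X18 - X0 on X0 is L x b - (1 - L). With b = 0 it is -(e/S)².

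**Rejection rate with b = 0.** The residual variance is 0.05² + e²(1 + L), and SE = sqrt(residual variance) / (S x sqrt(n - 2)). At e = 0.06:

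- sqrt(0.0025 + 0.0036 x 1.96) = 0.0978.
- n = 77: SE = 0.0978 / (0.30 x sqrt(75)) = 0.0376; z = -0.040 / 0.0376 = -1.06; Phi(-0.90) = 18%.
- n = 96: SE = 0.0336; z = -1.19; Phi(-0.77) = 22%.

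| e | L | null slope | SE (n = 77 / 96) | rejection at 0.05 | mean slope if b = +0.05 |
|---|---|---|---|---|---|
| 0.03 | 0.990 | -0.010 | 0.025 / 0.023 | about 7% | +0.040 |
| 0.045 | 0.9775 | -0.0225 | 0.031 / 0.028 | 11-13% | +0.026 |
| 0.06 | 0.960 | -0.040 | 0.038 / 0.034 | 18-22% | +0.008 |

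Simulation of the single-predictor regression agrees to within about one percentage point. At the two larger errors nearly all rejections are negative. At e = 0.06 the chance of passing the 0.2 level is 42-47%, against a nominal 20%.

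**Sensitivity to S at e = 0.06.** If 0.06 is the healthy SD and 0.27 the pooled SD with equal groups, the AD SD is sqrt(2 x 0.27² - 0.06²) = 0.38. The null slope is then -(0.06/0.38)² = -0.025, with a false-positive rate of about 13%. With S = 0.20 it is -(0.06/0.20)² = -0.09.

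**Other covariates.** If they explain 40% of baseline SUVr variance, the bias is divided by 0.6. At e = 0.05 it goes from -0.028 to -0.046.

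**Alternative outcome.** Use twice the month-9-to-18 change, which shares no scan error with X0, and assume even accumulation. The expected slope is L x b, which is zero when b = 0. Simulated false positives are about 5%. The residual variance is 0.05² + 8e². At e = 0.03, SE = 0.038 (n = 77) or 0.034 (n = 96). Simulated power for b = +0.05 is then about 25-31%, against 34-40% as planned. At e = 0.06 it is 11-12%, against about 4% in the right direction as planned.

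**The case against.** The strongest reply concerns size and importance. Every rejection rate rests on an assumed scan error and an assumed spread of true change. At e = 0.03 the bias is only about 0.4 SE, the false-positive rate is about 7%, and a true slope of +0.05 still averages +0.040. The two SDs come from a different region and reference method, and 0.06 in low-probability subjects need not bound the error in amyloid-positive patients. The calculation uses one predictor, whereas the plan selects among five. All of this stands. It limits the magnitude, not the direction.

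The model is also exploratory, and baseline SUVr is one of five candidates. The Confirmatory Cohort has no planned follow-up PET, so no SUVr-change result carries over into it. That also stands, although exploratory status does not move the null back to zero.

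Finally, the coefficient is valid for predicting observed change from a measured baseline scan. It misleads only when read as an effect of true tau on accumulation, which is how a reported associated factor is likely to be read.

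Three stronger readings are tempting and are not supported:

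- A reader might infer that the primary longitudinal result is compromised. It is not: the LS means of change, evaluated at the mean baseline, do not carry this bias.
- A reader might infer that a real positive relation will be hidden. Near-complete cancellation of +0.05 appears only at the largest error assumed here.
- A reader might infer that baseline SUVr must leave the model. As an adjuster it is legitimate: the other factors' coefficients equal those from regressing 18-month SUVr on baseline. Factors correlated with true tau keep a small bias. With a true-change SD of 0.06, n = 77 and correlation 0.5, false retention was 25% at e = 0.05, against a nominal 20%.

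**Conclusion.** The point holds for one coefficient. As planned, the baseline-SUVr estimate and p-value in the factor model are shifted downward by 1 - reliability, so they cannot be read as evidence on whether starting tau speeds or slows accumulation. That follows from the algebra for any independent scan error.

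The size cannot be taken from the documents. Under the stated assumptions it ranges from minor (e = 0.03) to enough to raise the false-positive rate at 0.05 about fourfold (e = 0.06). A smaller baseline SD in amyloid-positive subjects, or strong covariates, would make it worse; a larger SD would make it milder. The same structure is present in SAP 8.6.2.4.5, but no size was worked out there. This is a cheap improvement to an exploratory analysis, not a fault in the primary one.

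**What to change.** - In the SAP 8.6.2.1 factor model, keep baseline MUBADA SUVr as a fixed adjuster for the other factors. Do not report its coefficient or p-value as a factor associated with accumulation.
- Estimate the relation between starting tau and accumulation by regressing month-9-to-18 MUBADA SUVr change on baseline SUVr. As a sensitivity analysis, report the intercept-slope correlation from a random-slope model on all three scans.
- In SAP 8.6.2.4.5, keep the baseline score as an adjuster and do not interpret its coefficient as a factor for change.

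Cost: SAP wording and one further regression on scans already scheduled (SAP 4.3). The month-9-to-18 analysis needs a usable month-9 scan, describes only the second half of follow-up unless accumulation is even, and loses some power when scan error is low. The random-slope model treats time as linear, whereas the section's mixed model treats visit as categorical, which is why it is better kept as a sensitivity analysis.
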